14.8.1 Sensitivity Analyses for DOR

The analysis of DOR will be repeated on confirmed CR/PR according to RECIST 1.1 as adjudicated by IRC.

The analyses for DOR based on unconfirmed responses will be repeated for DOR based on confirmed responses (i.e. Kaplan-Meier analysis, listing of DOR, swimmer graph of time and duration of response in participants with confirmed CR/PR).

A large, stylized logo consisting of the letters 'C', 'C', and 'I' in a bright red color. The letters are bold and have a slightly irregular, hand-drawn appearance. They are set against a solid black rectangular background.

CCI

CCI

14.11 Overall Survival (Primary Endpoint)

The overall survival (OS) time is defined as the date from randomization to death due to any cause:

$OS = (\text{date of event/censoring} - \text{date of randomization} + 1) / 30.4375$ (months).

For participants alive at the time of data cutoff date or who are lost to follow up, OS will be censored at the last date known to be alive.

The date of event / censoring is defined in [Table 8](#).

Table 8 Survival Event / Censoring

Survival status	Date of event / censoring	Censoring
Participants alive or lost to follow-up before or at cutoff date	Last date known to be alive	Yes
Participants who died before or at cutoff date	Date of death	No

The following complete dates will be used to determine the last date known to be alive. Only the ones among them that are before or at data cutoff and which are not imputed shall be used in the derivation. Dates past the data cutoff will be ignored by the derivation:

- All participant assessment dates (blood draws (laboratory, PK), vital signs, performance status, ECG, tumor assessments, PRO assessments)
- Start and end dates of anticancer therapies administered after IMP discontinuation.
- AE start and end dates
- Last known alive date collected on the ‘Survival Follow-up’ eCRF (do not use follow-up date)
- IMPs start and end dates (including reinitiation of treatment)
- Randomization date
- Completion/Discontinuation date from the “Study Termination” eCRF page (do not use if reason for discontinuation is lost to follow-up or death)

Only dates associated with actual examinations of the participant reported in the eCRF will be used in the derivation. Dates associated with a technical operation unrelated to participant status such as the date a blood sample was processed will not be used.

The analysis of OS time will be performed with a Kaplan-Meier method with the same approach described for PFS in Section 14.4. Kaplan-Meier estimates (product-limit estimates) will be presented together with a summary of associated statistics including corresponding two-sided 95% CIs. They will be estimated at 12, 18, 24, 30, 36, 42, and 48 months.

A Cox’s regression model will be used with the same approach as for PFS described in Section 14.4.

The following null hypothesis will be tested:

$$H_0^{OS}: \lambda_M^{OS}(t) = \theta \lambda_P^{OS}(t), \theta \geq 1 \text{ versus } H_1^{OS}: \lambda_M^{OS}(t) = \theta \lambda_P^{OS}(t), \theta < 1$$

Where $\lambda^{OS}(t)$ represents the hazard at time t and θ the unknown constant of proportionality of hazards in the treatment arms M (M7824/bintrafusp alfa) and P (pembrolizumab).

H_0^{OS} will be tested according to the testing strategy described in Section 6.

Lan-DeMets alpha spending with O’Brien-Fleming-like boundaries will be adopted for the currently observed event size at cutoff date.

A participant listing will provide the following information: treatment arm, participant identifier, age, sex, race, date of randomization, date of event/censoring, event/censoring reason, and time to event.

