AE = adverse event; β-hCG = beta-human chorionic gonadotropin; CR = complete response; CRF = case report form; CRT = chemoradiotherapy; CT = computed tomography; D = Day; ECG = electrocardiogram; ECOG PS = Eastern Cooperative Oncology Group Performance Status; EoT = End-of-Treatment; HBV = hepatitis B virus; HCV = hepatitis C virus; ICF = Informed consent form; MRI = magnetic resonance imaging; PD = progressive disease; PE = physical examination; PR = partial response; RT = radiation therapy; T₄ = free thyroxine; TSH = thyroid-stimulating hormone; V = visit; W = Week; WOCBP = woman of childbearing potential.

Table 3 Safety and Long-term Follow-up – M7824 and Pembrolizumab Arms

M7824 and Pembrolizumab Assessment	Safety Follow-up Visit		Long-term Follow-up		Notes
	28 Days (± 5 days) after Last Treatment	12 Weeks (± 2 weeks) after Last Treatment	Every 6 weeks (± 1 week)	Every 12 weeks (± 1 week)	
Documentation concomitant therapy	X	X		X	
Documentation of AEs	X	X		X ^{a,b}	See Appendix 6 for safety recording and reporting and see Section 7.1 in case of discontinuation from the study intervention a: The 12-week Safety Follow-up and Long-term Follow-up may be conducted via telephone calls b: See Section 8.3.1 for definition of the AE Reporting Period and Section 8.3.3 for Follow-up of AEs/SAEs
Physical examination	X				Focused PEs to be performed as per local standard practice.
Skin assessment	X				
Vital signs	X				Including weight
ECOG PS	X				
12-lead ECG	X				
Hematology and hemostaseology	X				Details on blood tests under this category are listed in Table 16 . Samples must also be drawn and results for core chemistry, hematology, and pregnancy test reviewed prior to dose administration
Full serum chemistry Panel A	X				See Table 16 for individual tests in each laboratory panel.
Urinalysis	X				
β-hCG pregnancy test	X				β-hCG should be determined from urine or serum.
Free T ₄ and TSH	X				
Subsequent anticancer therapy (any line)	X	X	X		
Survival follow-up				X	

M7824 and Pembrolizumab Assessment	Safety Follow-up Visit		Long-term Follow-up		Notes
	28 Days (± 5 days) after Last Treatment	12 Weeks (± 2 weeks) after Last Treatment	Every 6 weeks (± 1 week)	Every 12 weeks (± 1 week)	

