- Treatment until confirmed progressive disease (PD) per Response Evaluation Criteria in Solid Tumors Version 1.1 (RECIST 1.1), unacceptable toxicity, or for up to 24 months. In the case of PD, treatment may continue past the initial determination of PD or confirmed PD if the participant's Eastern Cooperative Oncology Group Performance Status (ECOG PS) has remained stable, and if in the opinion of the Investigator, the participant will benefit from continued treatment and if other criteria are fulfilled as outlined in this protocol ([Sections 5.1](#) and [5](#)). Participants in either cohort who experience stable disease (SD), partial response (PR), or complete response (CR) should continue treatment until the end of 24 months, although additional treatment may be possible. If the Investigator believes that a participant will benefit from treatment beyond 24 months, it may be permissible after discussion with the Medical Monitor and the Sponsor Medical Responsible. Of note, pembrolizumab is only allowed for

24 months per regulatory (FDA, EMA) labels; therefore, extenuating circumstances and outstanding justification must be documented to support treatment beyond 24 months in either arm.

- Safety follow-up Visits until 12 weeks after the last dose of M7824 or pembrolizumab (Safety Follow-up Visit at 12 weeks is allowed via telephone call).
- Survival follow-up up to 5 years with visits (in person or by phone call) every 12 weeks after the last dose of M7824 or pembrolizumab unless reported as lost to follow-up, dead, or after study termination (recommended every 6 weeks on 2L treatment as below).

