OS	
 • OS IA and PA with cutoff when planned number of deaths is reached as planned in Table 12, while the alpha spending is adjusted according to Lan-DeMets with O’Brian-Fleming-like boundaries considering the total number of events planned for the primary analyses • OS analyses use a similar but reduced set of methods as applied for PFS. • OS is defined as the time from randomization to the date of death due to any cause. • For participants alive, the OS will be censored at the last date known to be alive.

Endpoint	Statistical Analysis Methods
	
 • Sensitivity analysis of OS will be done • Subgroup analyses as specified in the IAP including but not limited to: 
 • Histology • Smoking status • Asian versus non-Asian.
Secondary	
Objective response according to RECIST 1.1 assessed by IRC	
 • OR interim analysis is used for futility or respectively sample size adaptation decision – corresponding efficacy analyses are conducted on complete IRC read unconfirmed best overall response data of the first 100 randomized participants with cutoff 6 months after 100th participant randomization date (73-10 PD-L1 high population). IDMC will base decision to expand sample size on the crude ORR difference between treatment arms (ignoring randomization strata) • ORR – the rate of participants having an objective response, i.e. at least one overall assessment of CR or PR (before progression and before the start of a new anticancer treatment) will be calculated along with the corresponding 2-sided exact Clopper-Pearson 95% CI per treatment group. • Difference in ORR is estimated based on Cochran-Mantel-Haenszel method (taking into account the randomization strata) and test statistics will be presented. Odds ratio is estimated based on logistic models for objective response. Logistic models will be fitted with the endpoint as dependent variable, subgroup, treatment, and with and without the treatment by subgroup interaction as explanatory variables. • Sensitivity analyses including but not limited to: 
 • Investigator read data. • Confirmed objective response

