* Efficacy analysis will be provided in addition to outputs for regular IDMC safety meetings only for efficacy assessments IDMC meetings.

Data handling after cutoff date:

Data after the cutoff will not be displayed in any listings or used for summary statistics, e.g. laboratory values of samples taken after data cutoff, AEs with onset date after data cutoff, etc. will not be included in any analysis or listing.

Stop dates are not affected by this rule, e.g. a stop date of AEs, which starts prior to the cutoff, but stopped after date of cutoff, will not be changed.

Data cut will occur before the analysis database creation process, i.e. on the SDTM in input to the process for the ADAM creation.

Pooling of centers:

Because of the high number of participating centers and the anticipated small number of participants randomized in each center data will be pooled across centers, and the factor center will not be considered in statistical models or for subgroup analyses.

Unscheduled assessments

As per database definition, the unscheduled safety assessments are always linked to a scheduled time point (each unscheduled assessment is linked to the previous scheduled time point). Safety data retrieved from an unscheduled time point (vital signs, ECG and laboratory data) will be analyzed according to the following scenario:

- For shift tables, they will be taken into account in the definition of the worst assessment during the study
- For description at each time post-baseline point, the first available result (in chronological order) will be taken into account in the analysis in case of multiple values.

For description at baseline, the last available result before randomization will be taken into account in the analysis in case of multiple values.

Presentation of continuous and qualitative variables:

Continuous variables will be summarized using descriptive statistics, i.e.

- number of participants (N), number of participants with missing values
- mean, standard deviation (StD)
- median, 25th Percentile - 75th Percentile (Q1-Q3),
- minimum and maximum.

If there are no missing values this should be indicated by a 0.

Qualitative variables will be summarized by counts and percentages.

Unless otherwise stated the calculation of proportions will be based on the number of participants of the analysis set of interest. Therefore, counts of missing observations will be included in the denominator and presented as a separate category.

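### The OS censoring rule in SAP 14.11 drops proof of survival at the cutoff but keeps deaths up to it, so Kaplan-Meier OS tends to be too low in both arms

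*SAP*

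**What the plan says.** For living participants SAP 14.11 states that "OS will be censored at the last date known to be alive". Only actual, non-imputed dates on or before the cutoff qualify, and "Dates past the data cutoff will be ignored by the derivation". Table 8 treats "Participants who died before or at cutoff date" as events on the date of death and sets no limit on when the death had to be learned.

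Protocol Table 14 (Section 9.4.1) has the same basic rule, "For participants alive, the OS will be censored at the last date known to be alive", and is silent on contacts after the cutoff. SAP Section 9 has a general rule: "Data after the cutoff will not be displayed in any listings or used for summary statistics". It also places the cut early: "Data cut will occur before the analysis database creation process".

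On treatment, visits follow dosing, every 2 weeks (M7824) or 3 weeks (pembrolizumab). Off treatment, Protocol 4.1 plans "Survival follow-up up to 5 years with visits (in person or by phone call) every 12 weeks after the last dose", and the same sentence recommends a 6-week interval during second-line treatment. Protocol Table 3 allows a window of 1 week either side of the 12-week contact and collects subsequent anticancer therapy every 6 weeks.

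No section moves a participant known to be alive after the cutoff up to the cutoff date, and none describes a survival-status sweep at the cutoff.

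**The concern.** Take two participants last seen 10 weeks before the cutoff, both followed up 2 weeks after it. One died a week before the cutoff and counts as a full event. The other is alive, and the 10 weeks survived are discarded. Whether time in the last contact interval counts depends on the outcome, so the censoring is informative. The risk sets near the cutoff are too small for the deaths placed in them.

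OS is a primary endpoint, and SAP 14.11 reports Kaplan-Meier estimates from 12 to 48 months. The reverse Kaplan-Meier follow-up time in SAP 14.11.2 uses the same dates, so it is shortened too. After the recommendation to terminate, SAP 6.6 leaves one analysis that includes OS, with no later planned analysis to correct it.

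**Working it through.** **The plan's own figures.** The plan gives no figure for this bias. Its OS boundaries (SAP Table 3) do reproduce, with Lan-DeMets O'Brien-Fleming-type spending at one-sided 0.02 and critical HR = exp(−2z/√d). For N=300 this gives p 0.01202 and 0.01658 with HR 0.707 and 0.738, against 0.01201, 0.01658, 0.71 and 0.74 in the table. Those figures are not in dispute.

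**Why the hazard rises.** For an exponential model the hazard is deaths divided by person-time. The SAP rule leaves known deaths D unchanged but removes the total gap L between last contact and cutoff, summed over survivors. The overstatement is therefore T/(T − L), where T is person-time to death or cutoff.

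**Assumptions (not in the documents).** n=300; exponential OS with median 20 months, so λ = ln 2/20 = 0.03466 per month; uniform accrual over 24 months; exponential treatment duration with median 7 months, capped at 24. On-treatment contact intervals are from the protocol. Off-treatment contact is every 12 weeks or, alternatively, every 6 weeks for everyone. All survivors can be contacted after the cutoff.

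**Expected deaths.** With the cutoff at C months from first enrolment, the mean proportion alive is [exp(−λ(C−24)) − exp(−λC)]/(24λ). This gives 0.679, 0.551, 0.448 and 0.364 at C = 24, 30, 36 and 42, or about 96, 135, 166 and 191 deaths.

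**Hazard overstatement by simulation** (late deaths are those between the last pre-cutoff contact and the cutoff):

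| C (months) | Deaths, about | 12-weekly, all late deaths known | 6-weekly, all late deaths known | 12-weekly, half of late deaths known |
|---|---|---|---|---|
| 24 | 97 | 6.8% | 3.9% | 3.3% |
| 30 | 134 | 5.0% | 2.6% | 2.4% |
| 36 | 166 | 3.6% | 1.8% | 1.8% |
| 42 | 191 | 2.7% | 1.4% | 1.4% |

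If no late death is known, the ratio is 0.999 to 1.001, that is, no bias. Repeats of the 12-weekly case gave 6.5% at about 96 deaths, 5% at 134 and 3-4% at 191.

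**Hand check.** At C = 24, T = 96.3/0.03466 ≈ 2,779 months and 204 people are alive. An overstatement of 6.8% requires L = 2,779 × (1 − 1/1.068) ≈ 177 months. That is 0.87 months per survivor, or 0.87 × 30.4375/7 ≈ 3.8 weeks. This lies between the average on-treatment gap (1 to 1.5 weeks) and the average 12-weekly gap (6 weeks), as it should with survivors in both states. At C = 42, T ≈ 5,507 months and 109 are alive; 2.7% requires about 145 months, or 5.8 weeks each, consistent with few still on treatment.

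**Reported estimates** (all late deaths known). With 12-weekly contact at about 97 deaths, median OS is 18.4 instead of 19.4 months, and 18-month OS is 50.8% instead of 53.5% (true value 53.6%). At about 134 deaths the median is 19.3 instead of 20.3 months. At about 191 deaths the median hardly changes. With 6-weekly contact at about 96 deaths the median is 18.9 instead of 19.5 months.

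**At the planned OS event counts.** A second simulation set cut the data at the planned death counts, with control-arm OS set from the 70% one-year figure in Protocol 2.2 and 12-weekly contact off treatment. The hazard was 1.8-3.3% too high at 169 deaths and 1.1-2.2% at 197 (N=300), and 2.8-5.1% at 270 and 1.6-3.1% at 339 (N=584). At an assumed 100 of 300 deaths it gave 5-9%. That set includes scenarios with no survivor on treatment, so its upper end is a worst case.

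**Hazard ratio.** It moved by about 1% or less throughout, including with median treatment durations of 8 against 4 months.

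**The case against.** The case on the other side has real force.

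- *The gap is often shorter than 12 weeks.* Second-line follow-up is recommended every 6 weeks, and SAP 14.11 also accepts subsequent-therapy, AE, laboratory and tumour-assessment dates as alive dates. This stands: a reader might infer that everyone off treatment loses up to 12 weeks, but that applies only to those in survival follow-up alone.
- *The bias needs late deaths to be known.* Neither document gives the lag from cutoff to extraction, and many off-treatment deaths are learned at the same contact that would show survival. This stands too: the bias is conditional and can fall to zero.
- *The larger figures are not at a planned OS analysis.* Correct. At 197 deaths the median is 0-0.25 months shorter and 30-month OS 0.0-0.6 points lower, even with 12-weekly contact and all deaths known. A reader might take the SAP 6.6 analysis to be immature, but that section gives neither a death count nor a cutoff date.
- *Inference is unaffected.* Correct. Because contact spacing differs by arm, a reader might infer a biased hazard ratio or a compromised test. The calculations do not show it: boundaries, event triggers and the log-rank comparison stand.
- *The rule is prespecified and agrees with the protocol.* Also correct; this is not a contradiction between documents. But the agreement does not remove the unequal treatment of deaths and survivors, and no other provision does.

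**Conclusion.** The rule as written censors informatively. To the extent that late deaths are in the database at extraction, it lowers Kaplan-Meier OS, medians and landmark rates in both arms and shortens the reported follow-up time. Under the stated assumptions, with n=300 and all pre-cutoff deaths known, the hazard is overstated by about 4-7% at roughly 97 deaths, 3-5% at 134 and 1-4% at 191-197. The lower ends reflect 6-weekly contact, and less complete death reporting takes the bias toward zero. If the SAP 6.6 analysis is immature, the bias is at the upper end. The damage is to descriptive estimates of a primary endpoint, not to the test. The change is worth making because it is cheap and the error runs in one direction.

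**What to change.** Add two lines to Table 8 in SAP 14.11:

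1. A participant with a qualifying alive date after the cutoff, or a death date after the cutoff, is censored at the cutoff date.
2. Every other participant not known to have died is censored at the last date known alive on or before the cutoff.

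Derive the flag before post-cutoff records are removed from SDTM, and state it as an exception to the cutoff rule in SAP Section 9. It brings no post-cutoff event or follow-up time into the analysis; it only records that the participant was alive on the cutoff date.

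The cost is the SAP text, one derived flag and a small programming exception. No new visits are needed, because survival contacts are already scheduled. The benefit is limited to participants with post-cutoff information at extraction, and it relies on deaths and alive contacts being about equally complete. With 25% of late deaths unreported and 10% of survivors unreachable, the SAP rule still overstated the true hazard by about 5%, while the changed rule was within about 1%. A survival-status sweep at the OS cutoff would tighten this further, but it is extra site work and the fix does not depend on it.

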14.11.2 Follow-up time since randomization

A Kaplan-Meier analysis will be performed on follow-up time using OS data by reverting the censoring flag (participants still alive or lost to follow-up are counted as events, deceased participants are counted as censored). Kaplan-Meier estimates (product-limit estimates) will be presented by treatment arm together with the median time of follow-up. In particular, the follow-up rates at 3, 6, 9, 12 and 24 months will be estimated with 95% CIs.

15 Safety Analyses

The subsections in this section include specifications for summarizing safety endpoints that are common across clinical studies such as adverse events, laboratory tests and vital signs. Baseline values for safety analysis are defined in Section 9 of this IAP “Definition of baseline and change from baseline”.

15.1 Adverse Events

Treatment emergent adverse events (TEAEs) are those events with onset dates occurring during the on-treatment period (as defined in Section 9 of this IAP) or if the worsening of an event is during the on-treatment period.

Changes in toxicity grade, seriousness or outcome of AEs are recorded as separate entries in the eCRF with associated end and start dates (start date equals end date of previous entry). Such entries reporting the same event in such immediately consecutive periods will be considered as one event in the analysis. These events will be kept as separate records in the database in order to maintain the full detailed history of the events. The start date of the initial record in the sequence is taken as start date of the entire event, similarly the end date of the last event in the sequence is taken as end

date of the entire event. The overall outcome of the adverse event is the outcome of the last event in the sequence. Duration of the AE and the TEAE flag will be adjusted accordingly in the analysis.

All analyses described in this section will be based on TEAEs if not otherwise specified and will be described by treatment arm. The AE listings will include all AEs (whether treatment-emergent or not). AEs outside the on-treatment period will be flagged in the listings.

Incomplete AE-related dates will be handled as stated in Section 9.

Related Adverse Events are those AEs with relationship to IMP reported by the investigator as related (i.e. answer to the questions “Relationship with study treatment” = “Related” on “Adverse Event Details” eCRF page) and those of unknown relationship (i.e. no answer to the question “Relationship with study treatment”).

Serious Adverse Events (SAEs) are those events reported on the “Adverse Event Details” eCRF page with the “Serious Adverse Event” field ticked “Yes”.

Adverse Events Leading to Temporary Discontinuation are those events leading to temporary discontinuation of study treatment (answer to the question “Action(s) taken with study treatment” includes “Drug interrupted” on “Adverse Event Details” eCRF page).

Adverse Events Leading to Permanent Treatment Discontinuation are those events leading to permanent discontinuation of study treatment (answer to the question “Action(s) taken with study treatment” includes “Drug withdrawn” on “Adverse Event Details” eCRF page).

Adverse Event Leading to Death: AEs leading to death (as recorded on the “Adverse Event Details” eCRF page, change in grade = “No” and outcome = “Fatal”, or grade = “Grade 5 or death related to AE” or serious adverse event = “Yes” and seriousness criteria include “Results in death”).

Bleeding events are those AEs belonging to the MedDRA SMQ Haemorrhage terms (excluding laboratory terms).

Adverse Events of Special Interest (AESI): AESI will be identified according to a pre-specified search list of MedDRA Preferred Terms.

Categories of AESIs include (see details in Section 15.2.3):

- Infusion-related reactions (IRRs)
- Immune-related adverse events (irAEs)
- Skin AE possibly related to TGFβ inhibition
- Anemia.

